### Subject Questionnaires

Self-report about race and ethnicity

Self-report of socioeconomic status

International Physical Activity Questionnaire (IPAQ) ([www.ipaq.ki.se](http://www.ipaq.ki.se)) [98]

Handedness questionnaire [99]

Apathy Screen [95]

Need for Cognition Scale [100]

Mindful Attention Awareness Scale [101]

Detailed Protocol: SAGE

Quality of Life Scale (QOL) [102]  
Pittsburgh Sleep Quality Index [103]  
SF-36(tm) Health Survey [104, 105]

#### Pre-Intervention Assessment: Session 2

Session 2 will start in the ERP laboratory at [name].

#### Blood Samples

Subjects will be escorted to the phlebotomy lab at the BWH Center for Clinical Investigation, [name], which is in the same building as where our offices are located. They will be given the opportunity to sit quietly in the waiting area for ~10 minutes before being escorted to a phlebotomy room. Blood samples will be taken via a cannula inserted into a vein by a BWH phlebotomist. Approximately 35 ml of blood will be collected.

Approximately 10 ml of blood will be prepared according to the method recommended by the [name] Laboratory, Medical University of South Carolina.

In brief, one vacutainer tube with ~10 ml of whole blood is collected. This collection of blood will yield eight Eppendorf tubes with about 0.5 ml of serum in each. Another Eppendorf tube will contain the buffy coat (if available), and the vacutainer tube will contain the blood clot.

In the event that the BWH Center for Clinical Investigation is unavailable for blood processing and packaging, the sample will be taken to the Clinical Trial Center at BWH, where processing and packaging will be completed.

After freezing / storage, four of the Eppendorf tubes of serum, as well as one Eppendorf tube containing buffy coat, and the vacutainer tube containing the clot will be sent on dry ice by overnight mail to the [name] Laboratory, [name], Medical University of South Carolina, [name].

The remaining four Eppendorf tubes of serum will continue to be stored at BWH until the [name] Lab confirms receipt of the specimens. If the [name] lab does not require these tubes, they will be transported to the [name] Lab at Brigham and Women's Hospital and stored at BWH/Harvard-Partners Center for Genetics and Genomics, [name] (see below).

To prepare the serum, the blood first stays for 30 minutes at room temperature and is then centrifuged (at 4° C) for 10 minutes. The serum is then collected in a separate polypropylene container, mixed by inverting several times, and finally distributed into eight Eppendorf tubes, with 0.5 ml of serum in each. These will be kept frozen in Ziplock bags at -70° to -80°. The clot and the buffy coat (if available) will also be frozen and sent to the [name] Lab.

Additional blood will be collected and stored for future analyses, if/when additional funding becomes available. Approximately 5 ml will be collected (EDTA tube) for potential genetic analysis (identifying genetic variants that may impact age-related cognitive decline), and 20 ml will be collected (Lithium heparin tube) for purification and cryopreservation of peripheral blood mononuclear cells (PBMCs) from which epigenetic factors and markers of immune function can be derived. Preparation of blood products will be done by the

## Detailed Protocol: SAGE

[name] Lab at Brigham and Women's Hospital, and stored at BWH/Harvard-Partners Center for Genetics and Genomics, [name]. In the future, stored blood products may be sent for analysis at the Broad Institute at MIT or similar facilities that collaborate with BWH researchers. The informed consent forms will seek permission to store blood samples indefinitely for future study.

### ERPs

Subjects will then participate in ERP experiments while data on brain waves are being collected. An ActiveTwo electrode cap (Behavioral Brain Sciences Center, Birmingham, UK) will be used to hold to the scalp a full array of 128 Ag-AgCl BioSemi (Amsterdam, The Netherlands) "active" electrodes whose locations are based on a pre-configured montage. Electrodes are arranged in equidistant concentric circles from the 10-20 system position Cz. In addition to the 128 electrodes on the scalp, 6 mini bio-potential electrodes will be placed over the left and right mastoid, beneath each eye, and next to the outer canthi of the eyes to check for eye blinks and vertical and horizontal eye movements. EEG activity will be digitized at a sampling rate of 512 Hz.

During the experimental protocols, visual or auditory stimuli will be presented. Participants will be asked to respond to designated stimuli by button press or foot pedal. Visual stimuli will include simple geometric shapes, letters, and complex figures that are presented on a high resolution monitor. Auditory stimuli will be presented binaurally at between 75dB SPL and 90dB SPL through high quality headphones.

The protocols will assess electrophysiological responses to novelty processing (subject-controlled novelty oddball task), working memory/attention (n-back task), and visual and auditory perception (visual and auditory evoked potential studies). Before beginning any new experimental condition, subjects will be given step-by-step explanations of what to do. Subjects will participate in practice trials. A brief break will occur between each block, and longer breaks will take place between each experimental condition.

Subject-controlled Novelty Oddball Task: The experimental procedures for the Novelty Processing Task are analogous to the ones described in published reports [74, 75]. Two hundred and fifty line drawings, white on black background, will be presented in 5 blocks of 50, each at the center of a high-resolution computer monitor. All stimuli will subtend a visual angle of approximately 2.75° along their longest dimension. There will be three categories of visual stimuli: 1) a repetitive Standard Stimulus (a triangle)--70% frequency, 2) a Target Stimulus (upside down triangle)--approximately 15% frequency, and 3) Novel Stimuli, randomly drawn from a set of unusual/unfamiliar line drawings (e.g., impossible or fragmented objects) shown only one time each--approximately 15% frequency, many of which come from the collection of drawings that have been used by Kroll and Potter (1984) [106] and Kosslyn et al. (1994) [107]. Stimuli will appear within a fixation box, subtending a visual angle of approximately 3.5° x 3.5°, that remains on the screen at all times. Participants will be told that the study is investigating how people look at different kinds of line drawings. They will be viewing a set of drawings and can look at each picture for however long or short they like. They control the viewing duration by pressing a button (with their dominant hand) that leads to the erasure of the current stimulus and the onset of a blank screen, followed by the presentation of the next stimulus. Participants will be told that they will not be asked questions about the drawings at the end of the experiment. Also, participants will be told to respond to the designated target stimulus by pressing a foot pedal (ipsilateral to the button press). Instructions will indicate that accuracy is more important than speed.

## Detailed Protocol: SAGE

N-Back Task: The experimental procedures for the N-Back Task are analogous to the ones described in a previous report [108]. Subjects will perform a verbal *n*-back paradigm in the visual modality with three levels of difficulty (0-back, 1-back, 2-back). Stimuli will consist of letters of the alphabet, white on a black background, presented at the center of a high-resolution computer monitor for 200 ms, in pseudo-random order. Under each *n*-back condition, subjects were shown a series of 300 letters, divided into three blocks. For each level of *n*-back, 75% of trials will be non-matches and 25% of trials will be matches. Subjects will be instructed to respond only to match letters (button press on a game controller). Subjects will be told to respond as quickly as possible without sacrificing accuracy. The interval between the onset of consecutive visual stimuli will be fixed at 2200 ms. The hand used for button press and the order of *n*-back level will be counterbalanced across subjects.

### Evoked Potentials:

Visual evoked potentials: Subjects will be view a series of checkerboard stimuli (4° visual angle) flashed to the right or left visual field (presented at 1-9 Hz) while they fixate on a dot at the center of the screen.

### [74]ERP Recordings

ERP data collection and analysis will follow published reports by Daffner et al. (2012) [109]. An ActiveTwo electrode cap (Behavioral Brain Sciences Center, Birmingham, UK) will be used to hold 128 electrodes to the scalp. EEG activity will be digitized at a sampling rate of 512 Hz.

### ERP Data analysis

EEG data will be analyzed using ERPLAB and EEGLAB [110] toolboxes that operate within the MATLAB framework. EEG epochs for different stimulus types will be averaged separately. Although many event-related potentials (ERPs) will be measured, the focus of analysis will be on the P3b component, which reflects categorization/memory updating and the P3a component, which reflects orienting/executive control. The size of these components serves as an index of the amount of resources allocated to perform the task, and the latency of the component serves as an index of processing speed.

### Transcranial Doppler (TCD)

Information about blood flow using transcranial doppler (TCD), a non-invasive technique, also will be collected during an *n*-back task and in response to flashing checkerboard stimuli. TCD recordings will be done either before or after the ERP experiments.

Neurovascular coupling reflects the link between regional synaptic activity and regional cerebral blood flow. Under normal conditions, cerebral blood flow and cerebral metabolic rate are coupled, with an increase in metabolic demand leading to an increase in blood flow. Neurovascular coupling will be indexed by changes in bilateral middle cerebral artery blood flow velocities during the *n*-back task. A 2-MHz, pulsed flat transcranial Doppler probe (MultiDop, DWL) will be placed over each temporal bone. The signal on both probes will be range gated to a depth of 45 mm to 60 mm, to insure insonation of the M1 segment of the middle cerebral artery. Once the signals are maximized, the probe will be fixed in place for the duration of the test using a Velcro headband that will be placed over the ERP electrode cap. Localization and determination of the proper artery and position will be performed according to standard techniques. Normally, in about 1 out of 5 older people, these blood vessels cannot be tested.

### Baseline physical activity monitoring (accelerometry)

For the week between Session 2 at BWH and the start of the structured intervention in the homes of subjects, they will be asked to wear an accelerometer that is fitted snugly around the waist using the

## Detailed Protocol: SAGE

elastic waistband and is placed over the right hip. Subjects will be asked to wear the accelerometer while awake during 7 consecutive days, except during water based activities since the accelerometer is not waterproof. This will provide baseline data on the level of physical activity/movement in which subjects are engaged.

Accelerometry provides a physiometric measure of motor activity. The accelerometer is a lightweight, small (matchbox sized) non obtrusive device that measures and records accelerations. The accelerometer output is digitized by a twelve-bit Analog to Digital Converter (ADC) at a rate of 30 Hz. Once digitized the signal passes through a digital filter that band-limits the accelerometer to the frequency range of 0.25-2.5 Hz. The frequency range detects normal human motion and rejects changing accelerations within the passband.

### Interventions – General Features and Overview

All of the interventions will include the following features: the duration will be ~35 minutes per day, 5 days/week, over a 5 week period. A member of the research team will visit the subject's home to introduce the training program, and carefully review how to use the appropriate software on a computer, which will be loaned to subjects while they participate in the project. If the subject's home does not have internet access, the tablet provided will include prepaid wireless internet access. The team member will be present during a practice run to facilitate the process and address any concerns.

Subjects will be instructed to carry out the training sessions during the same part of the day (e.g., early morning), and to set up a routine in which they will not be disturbed by phone calls or visitors. Individuals will be told not train more than once a day. They will be encouraged to maintain their other activities and not substitute the training stimulation for another activity in which they have been routinely engaged.

For both cognitive and physical training, subjects will begin with a level they can easily manage. The difficulty will be slowly increased as their performance improves (due to training effects), with the aim of keeping the subjective effort approximately constant and moderately challenging through the 5 weeks. Similarly, for the mindfulness training, the meditations and tasks will become more self-directed and challenging during the 5 week course.

A member of the research team will communicate with each subject on a weekly basis (via phone call or email, whichever mode of communication is more convenient for the subject) to provide feedback and address any questions or concerns. Subjects will also be encouraged to contact the research team at any time they have questions or concerns. Data will be monitored for potential breaks, interruptions, and unusual performance fluctuations.

#### 1. Cognitive training using Cogmed (Pearson®)

During the initial session, a member of the research team will visit the subject's home and introduce the subject to the Cogmed training program ([www.cogmed.com](http://www.cogmed.com)). Individuals will start at the same low difficulty level. As training proceeds, task difficulty will be individually adjusted based on performance by increasing/decreasing the number of items individuals have to remember, such that a participant reaches approximately 60% correct per day for each task. Each training session will start at the task difficulty level where the participant ended in the previous session. Performance and reaction time data will be continuously recorded while subjects are doing the task, and these data will be sent via the internet to the research team after each session. A member of the research team will communicate with

## Detailed Protocol: SAGE

each subject on a weekly basis (via phone call or email) to provide feedback and address any questions or concerns.

### 2. Awareness (mindfulness) training

During the initial session, a member of the research team will visit the subject's home and introduce the subject to mindfulness techniques. For this training, subjects will participate in a series of mindfulness exercises. Before the start of each session, subjects will log-on to a secure password-required website. Each session will consist one fifteen minute guided mindfulness meditation that we will label "Mindfulness Meditation Session", and 3 six minute guided Mindfulness-in-Action tasks such as "mindful listening", "mindful observing", and "mindful walking," which we will label "Mindfulness Task 1", "Mindfulness Task 2", etc. The meditation and tasks will become increasingly more self-directed over the 5 weeks; the degree of guidance will decrease to keep the subjective effort approximately constant and moderately challenging through the 5 weeks.

The mindfulness meditations will be narrated by one guide and the tasks will be narrated by a different guide. We will have 7 mindfulness tasks in total, whose order of presentation will be counterbalanced across sessions: 1. mindful observing of place, 2. mindful eating, 3. mindful observing of object, 4. mindful observing of person, 5. mindful walking, 6. mindful listening, and 7. mindful writing with the non-dominant and dominant hand.

At the end of each session, participants will write brief reflections stored via the website (e.g., an estimate of the amount of time subjects experienced their thoughts as wandering) both as an integral part of the mindfulness process and as a means of increasing the likelihood that subjects fully participate in each session. Each session will be structured as follows: Login, Mindfulness Meditation Session, Mindfulness Task 1, Mindfulness Task 2, Mindfulness Task 3, Write Log Reflection, Logout.

Login and logout times will be recorded to keep track of a subject's participation. A member of the research team will communicate with each subject on a weekly basis (via phone call or email) to provide feedback and address any questions or concerns.

### 3. Physical exercise training using an interactive video platform

Subjects will participate in a structured physical exercise training program that aims to progressively increase their level of activity over the 5 week training period. During the initial session, a member of the research team will visit the subject's home and introduce the subject to the different aspects of the training program (e.g., interactive video, accelerometer). An interactive video will be used to present a structured exercise program. This interactive video is being created with exercise physiology specialists in Sweden. It will run using an application on the computer (connected to a monitor or TV screen if possible).

Each training session will begin with warm up/stretching exercises, followed by a series of aerobic exercises, with breaks every few minutes. The aerobic exercises will be followed by a cool down/stretching period.

## Detailed Protocol: SAGE

Aerobic exercises will include relatively low impact activities like walking, jogging, or running in place, which will aim to put limited demands on balance. Each exercise will be explained and demonstrated in the video. All exercises can be done standing, sitting, or next to a chair that provides balance support as demonstrated in the videos. After the first session, for each subsequent session the difficulty level will start at one level below the previous session's average difficulty level (e.g. if they exercise at the most difficult level for most of the time during one session, the next session will start at the medium difficulty level). Each exercise will be explained and demonstrated in the video.

There will be a water break every 8-10 minutes and an Exertion Check-In Break every 3-4 minutes. At each Exertion Check-In break, subjects will push one of 3 buttons to rate their perceived level of exertion ("Too Easy", "Somewhat Hard", "Too Hard"). If they choose "Too Easy", the next set of exercises will be a bit faster. If they choose "Too Hard", the next set of exercises will be a bit slower. If they choose "Somewhat Hard", the next set of exercises will stay at the same level. Subjects are told that the goal is to work at a level that requires a modest degree of effort, where they feel stimulated and like they are working hard, but not so hard that they feel dizzy or short of breath.

If they want to make the exercise easier or harder anytime, they can press the "Pause" button on the computer screen and choose "Too Easy" or "Too Hard".

If they would like a short break, they can also press the "Pause" button on the computer screen. When they are ready to start again, they can press the "Resume" button.

If they need to stop the exercise completely they can press the "Pause" button and then press "Start Over Later".

If, for some reason, they feel unable to carry out a particular exercise (e.g., inability to bend a knee because of arthritis), they will be able to press the "Pause" button and then the "Skip Exercise" button on the computer that will trigger the display and demonstration of an alternative exercise (e.g. Step Touch instead of Skipping).

For the five weeks-of the exercise training, during all waking hours –except during water- based activities- subjects will wear an accelerometer, as described earlier. The accelerometer will provide measurements of the intensity of physical activity during the exercise training and allow us to chart the degree to which it increases over the 5 week program. At least once a week-subjects will connect the accelerometer to an adapter attached to the computer. This will allow the accelerometer to be recharged and allow research staff to upload the, the activity data via the internet to our laboratory at BWH. Subjects will be given feedback about the amount of "activity units" that they have accrued during the training sessions, which will be automatically added to a log for their review that is stored on the computer. This will provide additional feedback to subjects about their progress and can serve to encourage them to increase the number of activity units per session over the course of their 5 weeks of training. A member of the research team will communicate with each subject on a weekly basis (via phone call or email) to provide feedback and address any questions or concerns.

#### 4. Low level of cognitive training using the Cogmed program (which will serve as an active control condition)

Individuals in the control group will participate in the same computerized Cogmed training program as described above. The main difference is that for the control group task difficulty will remain at the same low starting level, rather than increasing over time. The instructions given to subjects will be identical to the ones used in the cognitive training intervention. During the initial session, a member of the research team will visit the subject's home and introduce the subject to the Cogmed training program ([www.cogmed.com](http://www.cogmed.com)). As with the active training group, performance and reaction time data will be continuously recorded while subjects are doing the task and these data will be sent automatically to the research team after each session. A member of the research team will communicate with each subject on a weekly basis (via phone call or email) to provide feedback and address any questions or concerns.

#### Post-Intervention Assessment

Shortly after completing their 5 week intervention program, subjects will return to our BWH Lab at [name] for 2 half-day sessions. Every effort will be made to have the subjects return to the Lab within 2 days of completing the training program.

During these sessions, we will repeat the following measurements, as described in the section on pre-intervention assessment:

Collection of blood

Cognitive Testing (CANTAB subtests, *Trail Making Test*, Parts A and B, *Digit Symbol Coding*, *WAIS-IV*, *Controlled Oral Word Association Test (COWAT)*) [96, 97]

Completion of questionnaires

Neurologic/gait assessment

ERP studies

Transcranial doppler studies

Subjects will be paid for their time, as follows:

Pre-intervention evaluation session 1	\$60
Pre-intervention evaluation session 2	\$60
Structured intervention	\$30/week for 5 weeks
Post-intervention evaluation session 1	\$60
Post-intervention evaluation session 2	\$60
Completion of all study components	\$60

Subjects who choose to discontinue participation will be paid for their time in a prorated manner. Check request forms will be sent to BWH (accounts payable) and a check will be mailed to the address designated by the subject. During the evaluation session, the cost of parking will be covered by a voucher applicable to any BWH parking facility.

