### **Physical Activity**

Studies of animals have indicated that exercise promotes neurogenesis and synaptogenesis. Exercise up-regulates the production of brain derived neurotrophic factor (BDNF) [10, 11]. BDNF is believed to help induce neurogenesis and promote survival and/or neuronal differentiation. It has also been linked to long-term potentiation necessary for memory formation. A Cochrane Database System Review [12] noted that 8 out of 11 randomized controlled exercise intervention studies reported that structured aerobic exercise interventions resulted in increased cardiorespiratory fitness of the intervention group, with an average improvement of approximately 14%. This improvement was associated with better performance on cognitive functions, including auditory attention (effect size 0.52), speed of information processing (effect size 0.26), and visual attention (effect size 0.26).

Physical activity and exercise has been associated with the enhancement of cognitive and brain function, and with a reduced risk for clinical dementia [13-22]. A recent review article published in *Nature Reviews: Neuroscience* [23] concluded that physical activity improved cognition in both normal older adults and patients with early AD. Although benefits were seen for a range of cognitive functions, there appeared to be disproportionate improvement in executive control (including planning, working memory, and multi-tasking). Particularly intriguing are the exercise intervention studies that have looked at effects on not only cognition but also underlying brain structure and activity. For instance, in a study reported by Colcombe and colleagues [24], older individuals who participated in an aerobic training group exhibited significant increases in the size of components of the prefrontal cortex and superior temporal lobes. In another study by the same researchers [25], more physically fit older subjects as well as those randomly assigned to participate in the aerobic fitness training group performed better on an attention task (more efficient response to conflicting cues on a flanker task). Moreover, functional magnetic resonance imaging (fMRI) revealed that older subjects exhibited greater neural activity in regions associated with attentional control (middle and superior frontal gyrus, superior parietal lobule) and less activity in the anterior cingulate cortex.

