### **Specific Aims**

The overarching goal of the current study is to identify factors that promote neural plasticity and cognitive health in elderly persons.

The specific aims address the impact of different types of structured mental or physical stimulation over a 5 week training period on the following:

1. Biological markers of brain plasticity (e.g., BDNF)
2. Electrophysiologic markers (event-related potentials) of neural efficiency and capacity
3. Neuropsychological markers of cognitive performance
4. Vascular markers of cerebral health (e.g., neurovascular coupling using transcranial doppler)

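### The post-assessment has a soft 2-day maximum but no minimum after the last session, so for BDNF the design does not separate a last-bout effect from the 5-week effect

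*Protocol*

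**What the plan says.** **Timing of the post visit.** The Post-Intervention Assessment section says "Shortly after completing their 5 week intervention program, subjects will return to our BWH Lab", and then "Every effort will be made to have the subjects return to the Lab within 2 days of completing the training program". The first statement is general and the second is a target. Neither gives a shortest permitted interval.

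**Training.** Under Interventions – General Features and Overview, "the duration will be ~35 minutes per day, 5 days/week, over a 5 week period". The same section asks subjects to train at a constant part of the day and gives early morning as its example.

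**Blood.** The Blood Samples section says subjects will be "given the opportunity to sit quietly in the waiting area for ~10 minutes" before the draw. It sets no limit on earlier exercise and no time of day. At baseline the draw belongs to Session 2. The section on baseline accelerometry places a week between Session 2 and the start of training.

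**Aim and outcomes.** The Specific Aims concern the "impact of different types of structured mental or physical stimulation over a 5 week training period", and BDNF is the example given for the first aim. The Biostatistical Analysis section makes cognitive change scores the main outcomes and lists BDNF, gait, ERP and TCD changes as additional.

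**The concern.** The question asked is about five weeks of training. The post sample may be taken within hours of one training session, and the baseline sample cannot be. A change score then compares two samples taken under different conditions. For BDNF this matters most in the exercise arm, because only that arm has a programmed aerobic bout and the Protocol's Physical Activity section itself links exercise to BDNF production.

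If a single bout moves the marker for some hours, the exercise-versus-control contrast mixes that response with the training effect. Randomisation does not remove a measurement condition that arises after allocation and differs by arm. Adjustment for age or baseline performance does not remove it either.

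**Working it through.** **Step 1. Is there a lower bound anywhere?** The timing, blood-draw and intervention sections were read for one.

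| Section | What it fixes | Minimum interval after a session? |
|---|---|---|
| Post-Intervention Assessment | Target of 2 days at most | No |
| Interventions – General Features and Overview | About 35 minutes, 5 × 5 = 25 sessions, constant part of the day | No |
| Blood Samples | About 10 minutes of sitting | No |
| Pre-Intervention Assessment | Two sessions of 3 to 3.5 hours, on one or two days | No |

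A subject who trains early in the morning and attends the lab later that day complies with the plan.

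**Step 2. Is baseline comparable?** Session 2, which includes the draw, precedes training by about a week. No baseline sample can follow a programme bout. A subject's own habitual exercise is unrestricted before both draws, but that is not tied to allocation in the same way.

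**Step 3. Which measures and arms?** For BDNF, the exercise arm is the one with a programmed aerobic bout. Other measures are not confined to that arm. The Risks and Discomforts section says cognitive and awareness training can leave people tired or frustrated, and that muscle, joint or back discomfort can follow exercise. Cognitive tests, ERPs and gait are all repeated at the post visit, and all four arms share its window.

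**Step 4. Size, for illustration.** The Protocol states no SD, power, effect size or allocation ratio, so there is no figure of its own to reproduce. Assumptions:

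- 200 completers, both sites pooled, equal allocation: 200 / 4 = 50 per arm.
- True sustained effect zero; two-sided 5% test, so 2.5% in each direction.
- A last bout shifts the change score by *d* SD in a fraction *f* of the exercise arm. The documents give neither *d* nor *f*.

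Bias in the contrast = *f* × *d*. Standard error in SD units = √(2/50) = 0.20. Chance of a significant result in the direction of the shift = Φ(*f d* / 0.20 − 1.96). The small extra variance from mixing shifted and unshifted subjects is ignored.

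Example: *d* = 0.5, *f* = 0.5 gives a bias of 0.25; 0.25 / 0.20 = 1.25; Φ(1.25 − 1.96) = Φ(−0.71) = 24%.

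| *d* (SD) | *f* | Bias (SD) | Chance of a positive result |
|---|---|---|---|
| 0 | any | 0 | 2.5% |
| 0.2 | 0.5 | 0.10 | 7% |
| 0.2 | 1 | 0.20 | 17% |
| 0.3 | 0.5 | 0.15 | 11% |
| 0.3 | 1 | 0.30 | 32% |
| 0.5 | 0.5 | 0.25 | 24% |
| 0.5 | 1 | 0.50 | 71% |

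With 25 per arm (one site of 100 alone, 100 / 4), the *f* = 0.5 rows fall to 5%, 8% and 14%. A shift in the opposite direction would give the same chances of a spurious negative finding.

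**The case against.** **The mechanism is not in the documents.** The harm requires BDNF to move after one bout and to settle within the interval chosen. The Protocol gives a general link between exercise and BDNF, in a paragraph that opens with animal studies, and the Background mentions one human study with a positive effect. Neither separates an acute from a sustained response. This stands. A reader might infer that the exercise arm's BDNF result will be inflated; the documents support only that the two effects cannot be told apart.

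**It is not only the exercise arm.** A reader might infer that every measure is distorted in that arm alone. The Protocol's own account of fatigue and frustration after cognitive and mindfulness sessions rules that out. Only for BDNF is the one-arm reading defensible.

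**Ten minutes of sitting is not the only separation.** Post-visit measures are repeated as described for the pre-intervention assessment. If the baseline order is kept, blood comes in Session 2, after a Session 1 of 3 to 3.5 hours and travel from home, or on another day. This stands in part: the post-visit text does not restate the order, and some hours on the same day are still not a stated minimum.

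**Session times are largely captured.** Cogmed data are sent after each session, mindfulness logins and logouts are recorded, and the exercise arm wears an accelerometer. This helps a sensitivity analysis. It does not replace a design rule, because the interval is not randomised, and if nearly all subjects are seen soon after their last session there is little contrast to analyse.

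**A short window has a purpose.** It limits decay of a training effect, and visit details are often left to a manual. The first part is a reason to keep the upper bound. On the second, the Protocol does set this window, and sets only one side of it.

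**Conclusion.** The gap is certain: a soft maximum, no minimum, and no restriction on recent training before the assessment or the draw. For BDNF in the exercise arm, a last-bout effect and the 5-week effect named in the aims are not separated by design. Lesser after-effects of a session could reach cognitive, ERP or gait measures in any arm.

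The consequence is of unknown size and direction. The illustrative chances run from 2.5% (no transient shift) to 71% (0.5 SD in every exercise subject) and rest wholly on assumed shifts and fractions, equal allocation and 50 per arm. They show sensitivity and are not an estimate for this trial. Nor do the documents support reading this as a threat mainly to the main outcome: that is cognitive change, for which the Protocol offers only possible fatigue, frustration or discomfort. This is a worthwhile, inexpensive improvement to the protocol, not a flaw that invalidates it.

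**What to change.** In the Post-Intervention Assessment section:

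1. Set a minimum as well as a maximum interval from the last training session, identical in all four arms, and say to which of the two half-day sessions each bound applies. The documents give no basis for a particular length, so the study team should choose and justify it.
2. Allow no training session before testing on an assessment day.
3. Draw post blood at the same time of day, and at the same place in the session order, as that subject's baseline draw.
4. Record hours since the last session for every subject, in a common form across arms, for a sensitivity analysis of BDNF and the other outcomes.

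The cost is a scheduling instruction and one recorded item, much of which the training platforms already capture. The downside is a slightly tighter visit window.
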